### 6.3.10 Adverse Events

AEs data are collected on the 'Adverse Events' eCRF form.

AEs will be coded according to the Medical Dictionary for Regulatory Activities (MedDRA) system, the latest version and tabulated by System Organ Class (SOC) and by Preferred Term (PT).

A Treatment-Emergent Adverse Event (TEAE) is defined as an AE observed after starting administration of IMP or placebo (see Section 6.3.1).

TEAEs will be summarized by presenting, for each treatment regimen, the number of events and the number and percentage of patients with:

- Any TEAE
- Any Serious Treatment Emergent Adverse Event (STEAE)
- Any TEAE of Special Interest (TEAESI)
- Any TEAE related to IMP/Placebo
- Any TEAE leading to treatment discontinuation (drug withdrawn)
- Any STEAE related to IMP/Placebo
- Any TEAESI related to IMP/Placebo

The number and percentage of TEAEs by causality and the number and percentage of mild moderate and severe TEAEs will be tabulated by SOC, PT and treatment arm. All tables with TEAEs by SOC and PT stratified by treatment regimen will only be counted by patient once within each PT.

The following tables will be provided with TEAEs by SOC and PT stratified by treatment regimen: TEAEs, TEAEs related to IMP/Placebo, TEAEs leading to discontinuation, STEAEs, STEAEs related to IMP/Placebo, TEAESI and TEAESIs related to IMP/Placebo.

TEAEs, STEAEs and TEAESIs will be tabulated by severity (mild, moderate or severe) and relationship to treatment (No: not related, unlikely related, Yes: possible, probable and certain). If a patient has more than one event with the same PT, the AE will only be counted once and the worst/maximal severity and the worst/strongest relationship will be used.

A listing of all AEs will be presented, whether treatment emergent or not. TEAEs will be flagged in this listing. A separate listing for deaths, STEAEs, AESIs and TEAEs leading to discontinuation will be provided (if any).

The following AEs (SOC, PT) of special interest (AESI) will be evaluated by Investigators at all study visits and time points (as applicable):

- IOP rise over 30 mmHg (SOC- INVESTIGATIONS, PT-INTRAOCULAR PRESSURE INCREASED)
- Pain/discomfort associated with IMP instillation (SOC-EYE DISORDERS, PT-EYE PAIN, OCULAR DISCOMFORT and related with IMP)

SAF will be used for all AE related summaries.

As stated in the study protocol, treatment arms will be compared with respect to safety endpoints descriptively only. No further inferential comparison will be carried out.

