### **8.3.3 Recording Adverse Events**

Volunteered, observed, and elicited AEs will be recorded. This includes AEs the patient reports spontaneously, those the investigator observes, and those elicited in response to questions from the study staff. Patients will be asked open-ended questions, such as "How have you been feeling since your last visit?", at each study visit.

All AEs that occur during the study must be recorded in the AE section of the eCRF. All AEs eCRF entries should contain a brief description of the event, date and time of onset, duration, intensity, treatment required, relationship to study medication, action taken with regard to study medication, outcome, and whether the event is classified as serious.

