### **8.3.9 Adverse Events of Special Interest**

The following AEs (SOC, PT) of special interest (AESI) will be evaluated by Investigators at all study visits and time points (as applicable):

- IOP rise over 30 mmHg
- Pain/discomfort associated with IMP instillation

An AESI may or may not be serious. Nevertheless, the investigator is responsible for ensuring that all AESIs are reported to the Sponsor immediately, but in any event no later than 24 hours of any site staff becoming aware of the event. Further instructions on how to report AESIs will be provided separately.

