### 14.3 SAFETY DATA

#### Adverse events

Table	Title	Pop	Top.Line
14.3.1.1	Summary of Treatment Emergent Adverse Events (TEAEs)	SAF	X
14.3.1.2	Treatment Emergent Adverse Events by System Organ Class and Preferred Term	SAF	

14.3.1.3	TEAEs by SOC and PT by worst severity	SAF	
14.3.1.4	TEAEs by SOC and PT by worst relationship	SAF	
14.3.1.5	TEAEs related to IMP/Placebo	SAF	
14.3.1.6	TEAEs leading to discontinuation	SAF	
14.3.1.7	Serious TEAEs	SAF	
14.3.1.8	Serious TEAEs related to IMP/Placebo	SAF	
14.3.1.9	TEAEs AESI	SAF	
14.3.1.10	TEAEs AESI related to IMP/Placebo	SAF	
14.3.2	Listings of Deaths Other Serious Adverse Events, and Other Significant Adverse Events	SAF	

14.3.3 [This title is reserved for narratives.]

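### The SAP selects the instillation pain/discomfort AESI by two preferred terms plus relatedness, with no link to instillation and no stated reconciliation with the investigator AESI reports that the protocol requires

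*SAP*

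**What the plan says.** Protocol 8.3.9 names two AESIs. The one at issue is a clinical concept, "Pain/discomfort associated with IMP instillation", with no preferred terms and no relatedness condition. On reporting, "the investigator is responsible for ensuring that all AESIs are reported to the Sponsor immediately", and at the latest within 24 hours. The mechanics are deferred: "Further instructions on how to report AESIs will be provided separately".

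SAP 6.3.10 repeats the lead-in, "The following AEs (SOC, PT) of special interest (AESI) will be evaluated by Investigators at all study visits and time points (as applicable", and then adds an operational rule: "Pain/discomfort associated with IMP instillation (SOC-EYE DISORDERS, PT-EYE PAIN, OCULAR DISCOMFORT and related with IMP". It gives no other selection rule for this AESI. The same section sets the meaning of related: "relationship to treatment (No: not related, unlikely related, Yes: possible, probable and certain". SAP 8.1 plans Table 14.3.1.9 for all treatment-emergent AESIs and Table 14.3.1.10, "TEAEs AESI related to IMP/Placebo". SAP 6.3.10 also plans a tabulation of treatment-emergent AESIs by relationship to treatment.

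On data capture, Protocol 8.3.3 says "All AEs eCRF entries should contain a brief description of the event, date and time of onset, duration, intensity" and continues with treatment, relationship, action taken, outcome and seriousness. It names neither an AESI flag nor an item for association with instillation.

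**The concern.** The protocol asks which patients had pain or discomfort on instilling the drop, in the investigator's judgement. The SAP rule asks which patients had an event coded to one of two eye-disorder terms and judged related. These sets overlap but need not coincide, and the SAP does not say what happens when they differ.

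Tolerability is a stated objective in both documents, and this AESI is the only safety item defined by the act of instillation. The visit pain VAS and discomfort scale do not replace it. They are efficacy measures of symptoms after cataract surgery, and Protocol 5.2.1 keeps study medication out of the 30 minutes before a visit. If the AESI tables count something else, the plan has no dedicated summary of instillation tolerability.

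**Working it through.** The documents state no AESI rate or count, so there is no plan figure to reproduce. The check compares the two definitions.

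1. **Protocol set, P.** Events the investigator identifies and reports as instillation pain or discomfort (Protocol 8.3.9). Coding and causality grade are not conditions.

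2. **SAP set, S.** Organ class eye disorders, *and* preferred term eye pain or ocular discomfort, *and* related (SAP 6.3.10). Association with instillation is not a condition.

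3. **In P but not in S.** A reported AESI coded to any other preferred term or organ class fails the term condition. One rated unlikely fails the relatedness condition. Which other terms would be used, and how often, depends on coding practice that the documents do not describe.

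4. **In S but not in P.** Eye pain rated possible counts as related, and Protocol 8.3.4.2 allows that grade when disease or other drugs could also explain the event. Protocol 8.3.10 gives a concrete route: it expects ocular pain to accompany a rise in IOP. If that pain were recorded separately, coded as eye pain and rated related, S would count it although no drop provoked it.

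5. **All AESIs against related AESIs.** Let R be the related events. The rule for S requires membership of R, so S ∩ R = S. For this AESI, Table 14.3.1.10 must equal Table 14.3.1.9, and the No category of the tabulation by relationship must be empty. This follows from the wording alone. It does not apply to the IOP AESI, which carries no relatedness condition, so the two tables as a whole may still differ.

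6. **Arm wording.** The rule says related with IMP, whereas the neighbouring items in SAP 6.3.10 say IMP/Placebo. Read literally, it leaves unclear whether vehicle-arm events qualify.

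**Direction of error.** The two errors in steps 3 and 4 pull in opposite directions. As an illustration only, with rates that are assumptions and not in the documents, let r be the true rate, s the share of true events captured and f the rate of extra counts. Expected patients counted = N × (r × s + f). With N = 140 (active) and r = 5%, the true number is 140 × 0.05 = 7.0.

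- s = 50%, f = 0: 140 × 0.025 = 3.5
- s = 50%, f = 2%: 140 × 0.045 = 6.3
- s = 100%, f = 2%: 140 × 0.07 = 9.8

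Under the same assumptions in the vehicle arm (N = 70), the true number is 3.5 and the counts run from 1.75 to 4.9. Even the sign of the error is undetermined.

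**The case against.** The strongest reply is that nothing is set aside. The sentence introducing the SAP rule keeps evaluation with the investigators, relatedness is itself an investigator judgement (Protocol 8.3.4), and the protocol's lead-in already foresees coding by organ class and preferred term. The parenthesis may only supply the terms expected for an investigator-identified event. This stands to the extent that a reader might infer that the SAP discards the investigator's AESI report, and the documents do not say so. They are silent on how the report and the rule relate. That silence matters because the rule is the only one stated. Where the SAP wants reported status to govern it says so, as for rescue medication in SAP 6.3.9.

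A reader might also infer that the table will include unrelated events. It will not: events rated not related or unlikely are excluded. The possible extras are related events not tied to instillation, and two provisions limit them. Expected surgical pain is not recorded as an AE (Protocol Table 1, footnote 7), and clearly related signs and symptoms are to be grouped under one diagnosis where possible (Protocol 8.3.7), which would tend to absorb pain accompanying an IOP rise.

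It is fair, too, that an event associated with instillation will nearly always be judged related, so some overlap of the two tables follows from the concept. But the rule makes the overlap total and hides any exception.

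Finally, no event disappears. Every treatment-emergent event appears in Tables 14.3.1.2 and 14.3.1.4, related ones also in 14.3.1.5, and all AEs are listed. This stands and limits the consequence. A reader of those tables still cannot tell which events the investigator tied to instillation.

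**Conclusion.** The concern holds as a mismatch between the protocol's definition and the SAP's stated rule. Followed as written, the rule can miss reported AESIs and can count related eye pain unconnected with instillation. For this AESI the all-events and related-events tables are certain to be identical, and the not-related category is certain to be empty.

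The documents do not support a claim that the table *will* undercount, or by how much. They give no instillation-complaint rate and no coding distribution, and the two errors offset each other to an unknown degree. The figures in the check are illustrations, and the conclusion does not rest on them.

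The effect is limited to descriptive AESI outputs: SAP 6.3.10 plans no inferential safety comparison, and the primary and key secondary tests are untouched. The conclusion assumes that the rule in SAP 6.3.10 is what will be programmed, and that the separate AESI reporting instructions, which are not in these documents, do not already resolve the matter. It is worth correcting because the correction is cheap and tolerability is an objective.

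**What to change.** Before unmasking, amend SAP 6.3.10 as follows.

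- Define this AESI as any TEAE that the investigator reported as instillation pain or discomfort under Protocol 8.3.9, whatever its preferred term, and show the preferred terms within the table.
- Remove relatedness from the selection, so that Table 14.3.1.10 is a true subset of Table 14.3.1.9 and the not-related category can be populated.
- Keep the preferred-term list as a cross-check only. At the masked data review (SAP 6.2; Protocol 9.1.7 places it before database lock), compare it with the AESI reports, query the differences and list any that remain.
- Write IMP/Placebo in the rule, so that vehicle-arm events plainly count.

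The cost is SAP wording and a modest reconciliation. The main drawback is that no AESI flag is named among the eCRF fields, so AESI reports may have to be mapped to the AE dataset. Protocol 10.6 describes reconciliation between the safety and study databases for SAEs only, so this step would be additional. The completeness of the AESI reports is also unknown, which is why the term search should stay as a cross-check.

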### 6.3.11 Other Safety Assessments

#### Physical Examination

Full physical examination will consist of assessment of head, eyes, ears, nose throat, mouth, cardiovascular, respiratory, digestive, urogenital, musculoskeletal, nervous/psychological, endocrine/metabolic, hematologic, dermatological, allergies, immunological and other. The observed values for the physical examination will be recorded in the eCRF by the investigator as "normal" or "abnormal" and if abnormal, assessed as "clinically significant" or "not clinically significant".

The Investigator will perform full physical examinations at the Screening visit and at the Early Termination visit.

The investigator will perform physical examination following the usual standards of patients' examination at each study site.

#### Eye Examination

Pupil function, ocular alignment and motility, visual field by confrontation test, and anterior vitreous will be assessed for normality and clinically significance at the Screening visit and at the Early Termination visits.

#### Vital Signs

Vital signs will be assessed 15 minutes before any ocular assessment and at least  $30 \pm 10$  minutes before the first study medication administration. For all vital signs parameters (systolic and diastolic blood pressure, heart rate and body temperature) summary statistics will be produced for observed values by visit.

Vital signs data will be listed by patient. All clinically significant abnormal values will be flagged in this listing.

#### Indirect Ophthalmoscopy

Vitreous humor, central retina, peripheral retina, optic nerve disc and retinal vasculature will be assessed for normality and clinically significance at the Screening, Baseline, Visit 4, Visit 5 and at the Early Termination visit.

Outputs will be based on the SAF.

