Pain after ophthalmic surgery may be considered a sign of a possible complication. Severe pain is assumed to be a sign of postoperative inflammation or infection, making it a concern for both patient and physician. However, a surgery without perioperative complications may also be associated with significant postoperative pain during the early recovery. Thus, appropriate counseling and pain management should be provided to improve quality of life (6).

Also, uncontrolled inflammation may lead to serious side effects, such as posterior synechia, uveitis, cystoid macular edema or secondary glaucoma. Management of inflammation is thus a mainstay in modern cataract surgery (8). Despite surgical advances, post-cataract surgery inflammation is still a common cause of patient discomfort, delayed recovery and reduced visual outcome (9).

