##### **9.1.13.1 Other Safety Assessments**

- Physical and Eye Examination

Physical and eye examination data will be summarized for the safety population by each by randomized treatment group.

- Vital Signs

Vital signs will be summarized by treatment group, together with changes from baseline.

Shift tables will show the number of patients who changed from normal/abnormal at Baseline to normal/abnormal at each time of assessment.

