## 6 STATISTICAL AND ANALYTICAL PLANS

The planned tables and listings are presented in Section 8.

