### **Other Safety assessments**

Table	Title	Pop	Top.Line
14.3.4.1	Absolute and Percentage change from Baseline in Vital Signs by treatment regimen. Descriptive Statistics	SAF	
14.3.4.2	Summary statistics. Change from Baseline to Day 3, Day 8, Day 15 and Day 29 compared to placebo in intraocular pressure (IOP).	SAF	X

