### **Other Safety assessments**

Listing	Title	Pop	Top.Line
16.2.9	Vital signs	SAF	
16.2.10.1	Physical examination	SAF	
16.2.10.2	Eye examination	SAF	
16.2.10.3	Indirect Ophthalmoscopy	SAF	
16.2.11	IOP measurements by Goldman Tonometer	SAF	

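### The SAP only lists ophthalmoscopy, physical and eye examination results and omits the vital-sign shift tables, leaving parts of the planned safety assessment without a by-arm summary

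*SAP*

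**What the plan says.** SAP 6.3.11 describes indirect ophthalmoscopy in one sentence: "Vitreous humor, central retina, peripheral retina, optic nerve disc and retinal vasculature will be assessed for normality and clinically significance". It is done before treatment at Visit -1 and Visit 1, then again at Visits 4 and 5, and when a patient leaves the study early. The only statement about analysis is "Outputs will be based on the SAF". It names no count, shift or comparison. Protocol 8.1.2 gives the form of the data: each finding is normal or abnormal, and an abnormal finding is clinically significant or not.

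Section 6 of the SAP opens by saying where the outputs are defined: "The planned tables and listings are presented in Section 8". In Section 8.1 the other safety assessments have two tables. Table 14.3.4.1 is "Absolute and Percentage change from Baseline in Vital Signs by treatment regimen", and Table 14.3.4.2 covers intraocular pressure (IOP). In Section 8.2, "Indirect Ophthalmoscopy" is Listing 16.2.10.3, and the same data appear again as Listing 16.2.6.6 under efficacy. Physical and eye examination are Listings 16.2.10.1 and 16.2.10.2.

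Protocol 9.1.13.1 promises more for two of these assessments. Physical and eye examination data are to be summarised by randomised group in the safety population. For vital signs, "Shift tables will show the number of patients who changed from normal/abnormal at Baseline to normal/abnormal at each time of assessment". Protocol 7.4 and SAP 3.3 list change from Baseline, against placebo, in physical and eye examination parameters and vital signs as a safety endpoint.

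**The concern.** A listing shows individual patients. It gives no count by arm and no denominator of patients examined. If Section 8 is followed as written, the report will contain no by-arm summary of ophthalmoscopy, physical examination or eye examination. It will also not show how many patients in each arm moved from normal to abnormal vital signs.

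Ophthalmoscopy matters most here because, at scheduled visits, it is the only examination of the posterior segment repeated after dosing starts. Protocol 2.1 warns that "uncontrolled inflammation may lead to serious side effects, such as posterior synechia, uveitis, cystoid macular edema or secondary glaucoma". Those are consequences of inflammation left uncontrolled, so an excess could appear on placebo. Protocol 2.3 separately lists glaucoma among rare ocular events linked to corticosteroids, so an excess could also appear on active treatment. When the direction is open, counts in both arms are what a reader needs. Protocol 2.1.4 adds that the product has not been tested clinically in the proposed indications, and Protocol 2.2 says the study is meant to support a marketing application.

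**Working it through.** The plan gives no figure to reproduce. The check sets the promised outputs beside the planned ones, then asks how much the adverse event tables recover.

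**Step 1. Promised against planned.**

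| Assessment | Protocol 9.1.13.1 | Table in SAP 8.1 | Listing in SAP 8.2 |
|---|---|---|---|
| Indirect ophthalmoscopy | not named | none | 16.2.6.6, 16.2.10.3 |
| Physical examination | by-group summary | none | 16.2.10.1 |
| Eye examination | by-group summary | none | 16.2.10.2 |
| Vital signs | summary, change from baseline, shift tables | 14.3.4.1, no shift table | 16.2.9 |
| IOP | not named | 14.3.4.2 | 16.2.11 |

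Ophthalmoscopy therefore has 0 tables and 2 listings.

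**Step 2. Does a general rule fill the gap?** SAP 6.3.2 presents categorical data as counts and percentages, by group and visit where that applies. This would permit a table but does not create one, because Section 8 defines the outputs and contains none.

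**Step 3. Timing of the adverse event route.** SAP 6.3.1 counts an event as treatment-emergent if first dose date ≤ onset date ≤ last dose date. SAP 6.3.10 tabulates only treatment-emergent events by arm; other adverse events are only listed.

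- Planned doses: 56 (SAP 6.3.8), four a day, so 56 / 4 = 14 days. The last dose falls on Day 14, or on Day 15 if Day 1 holds fewer than four doses.
- Visit 4: Day 15 ± 2, that is Days 13 to 17.
- Visit 5: Day 29 ± 2, that is Days 27 to 31.

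| Last dose | Visit 4 days inside the window | Visit 5 days inside the window |
|---|---|---|
| Day 14 | 13, 14 (2 of 5) | none |
| Day 15 | 13, 14, 15 (3 of 5) | none |

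An abnormality dated to its discovery at Visit 5 is never treatment-emergent. One dated to Visit 4 is missed on Days 15 to 17 (last dose Day 14) or on Days 16 and 17 (last dose Day 15). For a patient who stops treatment early but keeps attending, the window closes earlier still.

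**Step 4. Does a finding become an adverse event?** Protocol 8.1.1 (physical examination) and 8.1.3 (vital signs) each say when an abnormal finding is reported as an adverse event. Protocol 8.1.2 (ophthalmoscopy) has no such rule. A finding graded abnormal but not clinically significant has no clear route into the adverse event tables.

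**Step 5. Can another examination stand in?** Protocol 8.1.1 includes a fundus examination in the eye examination at Visit -1, and Protocol Table 1 repeats the eye examination only at Early Termination. The SAP's own list of eye-examination items does not name the retina or optic nerve. At Visits 4 and 5, ophthalmoscopy stands alone.

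**The case against.** The strongest reply is that these abnormalities are not lost. Protocol 8.3.1.1 counts any unfavourable sign as an adverse event, 8.3.3 requires events the investigator observes to be recorded, and 7.5.2 sends significant medical events at later visits to the adverse event form. Treatment-emergent events are then tabulated by arm. This stands in part: a reader might infer that new retinal or optic nerve abnormalities are never counted by arm, and the documents do not support that. An abnormality reported as an adverse event with onset by the last dose is counted in Table 14.3.1.2. The route still leaves out the cases in Steps 3 and 4.

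The treatment-emergent window can also be disputed. SAP 6.3.10 describes these events more loosely, as observed after administration starts, and Protocol 9.1.13 tabulates all adverse events by group. But 6.3.10 refers back to 6.3.1, which contains the explicit date rule, and the SAP's tables are restricted to treatment-emergent events. The window is a separate matter that an ophthalmoscopy table would not repair.

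Nor does the SAP break a protocol promise on ophthalmoscopy. The protocol treats it in 8.1.2, apart from the eye examination in 8.1.1, and 9.1.13.1 does not name it. That stands. The departure from 9.1.13.1 concerns physical and eye examination and the vital-sign shift tables.

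Other data bear on the same harms. IOP has its own by-arm table, a rise over 30 mmHg is an event of special interest, and visual acuity is compared by arm. Protocol 9.1 has listings labelled by randomised group, so a reader could count by hand. All of this stands, and it rules out any claim that the report could say nothing about these risks.

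Two further arguments are tempting. One is that vital-sign shifts matter because corticosteroids can cause hypertension, but Protocol 2.3 ties that effect to long-term systemic exposure. The other is to size the gap by the chance of seeing a rare event among 140 active patients, but that chance is the same with or without a table.

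**Conclusion.** The point holds as an omission in the planned outputs. Three assessments (ophthalmoscopy, physical examination, eye examination) have no by-arm table, and vital signs lack the shift tables. For physical and eye examination and vital signs, the SAP falls short of Protocol 9.1.13.1 and of a safety endpoint that it restates itself. For ophthalmoscopy, abnormalities not reported as adverse events, or starting after the last dose, reach no planned by-arm table. That includes every abnormality first dated at Visit 5.

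This rests on two assumptions: that Section 8 is the full set of outputs, as the SAP says, and that onset is dated to discovery. An abnormality back-dated to on or before the last dose would be counted if reported. No event rate is assumed.

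The size is moderate. Efficacy conclusions are untouched and the data are collected. What is missing is a pre-specified by-arm count with a denominator. It is worth correcting before unmasking.

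**What to change.** In SAP 6.3.11 and 8.1, add one descriptive ophthalmoscopy table for the study eye in the safety set, by arm. For each of the five structures, classify status as normal, abnormal not clinically significant, or abnormal clinically significant. Show the shift from Visit 1 to Visit 4, to Visit 5, and to the worst post-baseline result including Early Termination, with n and percentage of patients examined. Exact confidence intervals are optional, since SAP 6.3.10 keeps safety comparisons descriptive.

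Add the vital-sign normal/abnormal shift tables and the by-group physical and eye examination summary of Protocol 9.1.13.1. Protocol Table 1 schedules the physical and eye examination only at Screening and Early Termination, so that summary can cover only those two visits, and the SAP should say so. Delete the duplicate ophthalmoscopy listing.

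The cost is a few lines of SAP text and two or three extra descriptive tables from data already collected. It needs no new assessments and no change to clinical management.
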